## **Statistical Methods**

Single factor ANOVA analysis will be used to determine if the extent of circumference reduction in the test group is statistically significant over changes in the control group. Additional correlation assessment will be performed to identify any potential relationships between patient data sets, and single-factor ANOVA assessment applied to those correlations as applicable. Missing or incomplete data shall be populated using least-favorable data from participants who did complete the study.

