## **STUDY OBJECTIVES**

**PRIMARY** - The primary objective of this study is to determine if the application of lower frequency (35kHz to 45kHz) ultrasound energy to the waist/abdominal region of the human body is capable of effecting a reduction in the amount of subcutaneous adipose cells and/or tissue to an amount of at least 1 inch and to a statistically significant level. Determination of the reduction in this adipose tissue is achieved via measurement of the body circumference that includes the abdominal area that was treated, and comparing measurements prior to the initial treatment with measurements after the entire treatment regime is concluded. Per the proposed clinical mechanism of action, the disrupted tissue is cleared by the lymphatic system which facilitates excretion or elimination of the disrupted tissue contents. Having been eliminated, the patient should exhibit a reduction in waist circumference. For this objective to be successfully achieved, a reduction in waist circumference of at least one inch must be demonstrated at a point of 12 weeks after the last of three treatment sessions has been applied.

**SECONDARY** - The secondary objective of this study is to assess the safety of this device. Assessment is made by having the patient rate the treatment experience and report any symptoms, side effects, or associated abnormal conditions. Additional assessment is made by the investigators to qualitatively confirm if visually detectable abnormal conditions (example: edema) are presented following the treatment. Success is determined by whether the patients indicate that any discomfort experienced during the treatment, and following the treatment that are directly attributable to the treatment, along with an absence of side-effects or abnormal conditions directly attributable to the treatment, create a risk/benefit condition where the benefit of treatment is regarded to outweigh the risks and temporary discomfort. Quantitatively, the benefit is regarded to outweigh the risk when: 1) No patients report a pain rating of 4 or higher on the Stanford Pain Scale, 2) No patients exhibit any side effects or abnormal conditions at the conclusion of the final treatment, and 3) No patient who was included in the Test group reports that the treatment regimen was unsuccessful.

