### **Statistical methods planned, including handling data exclusion, analysis of sub-groups if any**

Any patient that did not conclude all three treatments shall be excluded from the analysis. If there are fewer than 37 patients remaining after the study concludes and exclusions are applied, than no analysis shall take place and additional study subject enrolled until a minimum of 40 completed participants exist. In the event that a patient concludes at least one treatment session, but afterwards discontinues

participation in the study, the presence of the patient in the study shall be acknowledged for data analysis purposes. Missing data for such acknowledged participants shall be fulfilled by inserting the least favorable result obtained realized from among all test subjects who did complete the study. Statistical analysis shall then proceed on the fully populated study data.

Primary analysis shall consist of applying the Anova single-factor acceptance test evaluating the change in waist circumference based on the data collected by the tape measure. A confidence of  $P=0.05$  shall be applied. The results of this data shall be directly applied to determining if the primary objective of the study has been met.

A correlation analysis shall be applied to all variable data recorded, as well as key calculations from the data, to identify any potential two-way connections or relationships between sets of data. Any correlations scoring a magnitude of 0.85 or greater shall be discussed and if appropriate, Anova single-factor analysis applied to determine if there is statistical significance to the relationship and any statements that might be supported by the data. Of primary interest is any impact the starting BMI might have on the amount of change, and any impact that gender may impart to the outcome.

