### **Sample size**

A total sample size of a minimum of 40 patients was established for this study. This number is based on

$$n = \frac{2 \cdot (Z_\alpha + Z_\beta)^2 \cdot \sigma^2}{d^2}$$

where:

$Z_\alpha = 1.96$ , based on a confidence of  $P=0.05$  (false rejecting of a true null hypothesis),  
 $Z_\beta = 0.84$ , based on a power of 80% (failure to reject a false null hypothesis),  
 $d = 1.0$  inch reduction in waist circumference as a meaningful/successful change in measurement,  
 $\sigma = 1.50$  inches, based on the evidence presented by a published study under similar treatment parameters and conditions reporting a typical response of 0.75 inches through the umbilical region and assuming some of the population may not respond at all.

The resulting calculation gives a population size of 37. Accounting for possible attrition and adding a generous margin of safety, a recruitment size of 50 individuals is arrived at. Review of the data analysis shall be conducted by an independent entity to confirm the handling and calculation of data, and the conclusions drawn from the data regarding statistical significance.

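### Where the missing-data fill applies, copying the single worst completer result into each patient lost after a session can by itself decide the primary result, and with a control arm it is not reliably conservative

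*Combined protocol and SAP*

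**What the plan says.** Two places prescribe the fill. The Synopsis, under Statistical Methods, says: "Missing or incomplete data shall be populated using least-favorable data from participants who did complete the study". The Data Analysis part, under Statistical methods planned, limits it to patients who finish at least one session and later discontinue. Their gaps are closed by "inserting the least favorable result obtained realized from among all test subjects who did complete the study", and the analysis then runs on the completed data set. The primary single-factor ANOVA of change in waist circumference is described next.

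The result is held to a fixed threshold. Under Study Objectives, "a reduction in waist circumference of at least one inch must be demonstrated at a point of 12 weeks".

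On numbers, the Recruitment section aims for about 50 enrolled and at least 40 completing. The Sample size section says: "Accounting for possible attrition and adding a generous margin of safety, a recruitment size of 50 individuals is arrived at". No dropout rate is given.

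Two sentences point the other way. The opening sentence of Statistical methods planned drops anyone who did not have all three treatments, and Data quality assurance keeps the data of patients who discontinue out of the analysis.

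The design is also described in two ways. Study configuration calls the trial single-arm, while the title page and the Synopsis describe a control group. Under Details of the treatment protocol, the waist is measured before and after every session and again at the 1-, 4- and 12-week visits.

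**The concern.** The minimum of a sample is its least stable summary. With 40 completers and normal changes it lies on average about 2.2 SD below the mean, and one unusual patient or one bad tape reading can set it. The rule then gives that value to every filled patient, whatever the patient's own readings showed. Both the mean and the SD of the analysed data come to depend on how many patients left and on one extreme completer.

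In a single-arm trial judged against 1 inch, this pulls the reported mean down and can hide a real effect. In a two-arm trial the fill also goes to control patients. A poor value given to a control dropout moves the comparison towards the device, so a rule that looks cautious need not be.

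**Working it through.** **The plan's own figure.** With the Sample size inputs, n = 2 × (1.96 + 0.84)² × 1.50² / 1.0² = 2 × 7.84 × 2.25 = 35.28, which rounds up to 36. The t-distribution version gives 36.3, that is 37, so "The resulting calculation gives a population size of 37" is reproduced. The 1.0 inch and 1.50 inches are used below as true mean loss and SD of change.

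**Single arm.** Assumptions: 50 enrolled; m patients filled and n = 50 − m completers; normal changes with mean μ = 1.0 and SD σ = 1.5; dropout unrelated to outcome; the 1-inch criterion applied to the mean. Let k be the expected distance, in SDs, of the minimum of n normal values below their mean.

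- Expected worst value: W = μ − kσ
- Expected reported mean: (nμ + mW)/50 = μ − (m/50)kσ

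| Filled m | Completers n | k | W (inch) | Reported mean (inch) | Chance that mean reaches 1 inch |
|---|---|---|---|---|---|
| 2 | 48 | 2.233 | −2.35 | 0.87 | 27% |
| 5 | 45 | 2.208 | −2.31 | 0.67 | 8% |
| 10 | 40 | 2.161 | −2.24 | 0.35 | about 0.8% |

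For m = 10: W = 1.0 − 2.161 × 1.5 = −2.24, and (40 × 1.0 + 10 × (−2.24))/50 = 0.35. The last column is from simulation; completers alone reach 1 inch 50% of the time, because the true mean is set at the threshold. Simulation with m = 10 also gives a mean of 0.35 (central 95% of trials −0.19 to 0.88) and an SD of 1.87. Power of a one-sample test against zero is 29%, against 98% in completers only. The true loss would have to be 1 + 0.2 × 2.161 × 1.5 = 1.65 inches for the reported mean to average 1.0.

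**Sensitivity with 10 filled.** The reported mean is 1 − 0.2 × 2.161 × σ:

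- σ = 0.5: 0.78
- σ = 1.0: 0.57
- σ = 1.5: 0.35
- σ = 2.0: 0.14

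If the worst completer simply shows no change, it is (40 × 1.0 + 10 × 0)/50 = 0.80.

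**Two arms.** Assumptions: 25 per arm (no allocation ratio is stated), SD 1.5, no true effect, two-sided 5% t test (the same as a two-group ANOVA). The text does not say whether the worst value comes from all completers, from the test group or from the patient's own arm, so all three were simulated. Each cell gives the average false difference in inches (positive favours the device) and the false-positive rate in the device's favour (nominal 2.5%).

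| Dropouts test/control | Worst of all completers | Worst of test arm | Worst of own arm |
|---|---|---|---|
| 2/8 | 0.78; 25% | 0.70; 21% | 0.63; 25% |
| 3/7 | 0.52; 8.6% | 0.46; 8.1% | 0.42; 13.5% |
| 4/6 | 0.26; 2.0% | 0.23; 2.8% | 0.21; 6.6% |
| 5/5 | 0.00; 0.3% | 0.00; 1.1% | 0.00; 2.9% |
| 7/3 | −0.52; 0.0% | −0.44; 0.2% | −0.43; 0.5% |

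If *least favorable* means adverse to the device, so that control dropouts get the best control value, the 2/8 split gives −1.09 inches and virtually no false positives favouring the device. With a true difference of 1.0 inch and 5/5 dropout, the three fills report 0.80, 0.80 and 1.00.

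**The case against.** **The fill may not reach the primary analysis.** The exclusion sentences remove the same patients, and under exclusion this dilution does not occur. A reader might infer that every withdrawn patient is filled. The text does not support that: patients who leave before a first session are outside the rule, and the exclusion sentences conflict with it for the rest. This stands and limits the point to wherever the fill is applied. It does not remove it, because two sections prescribe the fill and settling the conflict in its favour would leave the defect in place.

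**The plan does not budget for 20% dropout.** A reader might take 50 enrolled and 40 completing as planned attrition and 0.35 inch as the expected result. But 40 is a minimum target, and the 50 includes a safety margin as well as attrition. This stands: 10 filled is one scenario, and 2 or 5 are equally compatible with the text.

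**The worst value may be much less extreme.** The Sample size section ties its SD to a typical response of 0.75 inch and an allowance for non-responders. That suggests worst results near zero rather than a gain of over 2 inches, and does not clearly make 1.5 inches an SD of change. This stands as a limit on size. Even a worst value of zero still takes a true 1.0 to 0.80 with 10 filled.

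**Worst-case filling is a recognised cautious choice.** In the single-arm reading the error runs against the sponsor and risks a missed effect, not a false claim. This stands and lowers the severity. It does not carry over to a controlled comparison with more dropout on control.

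**Conclusion.** The point holds for patients to whom the fill is applied, and should be fixed. In the single-arm illustration the reported mean falls from 1.0 inch to 0.87, 0.67 or 0.35 with 2, 5 or 10 filled. With 10 filled the range is 0.78 to 0.14 for SDs of 0.5 to 2.0, or 0.80 if the worst completer is unchanged. The rule alone can therefore make an effective device miss the criterion. It does not follow that the device is almost sure to miss: that needs about 10 filled patients and a normal lower tail at SD 1.5, neither of which the plan establishes.

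In the two-arm reading, 2 test and 8 control dropouts give a false benefit of about 0.6 to 0.8 inch and 21% to 25% false positives favouring the device. A reader might infer that control dropouts always inflate the benefit. They do not: equal dropout creates no false benefit on average, test-heavy dropout biases against the device, and reading the rule as adverse to the device removes the inflation. The documents give neither the split nor the allocation ratio.

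**What to change.** 1. Reconcile the exclusion sentences (Data quality assurance, and the opening of Statistical methods planned) with the fill in that section and in the Synopsis, so that all patients with at least one session enter the primary analysis. Unless this is done first, the model below would be barred from using their data. The item on failure to complete in the exclusion list should be aligned too.
2. Make the primary analysis a repeated-measures mixed model, or multiple imputation, that uses each patient's own baseline, session, week-1 and week-4 waist readings to handle a missing week-12 value.
3. Keep least-favorable insertion as a labelled sensitivity analysis. If there is a control arm, define it by arm: worst value for test dropouts, best value for control dropouts.

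The cost is wording in three sections and slightly more analysis work, with no new patients or measurements. The downside is that the primary result then relies on a missing-at-random assumption, which the retained sensitivity analysis tests.

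### Where the worst-completer fill is used, it also feeds the correlation, starting-BMI and gender analyses, in which a worst value is not conservative in any direction

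*Combined protocol and SAP*

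**What the plan says.** Under Statistical methods planned (DATA ANALYSIS), a patient who has at least one session and then discontinues stays in the data. The missing values are supplied by "inserting the least favorable result obtained realized from among all test subjects who did complete the study". The next sentence reads "Statistical analysis shall then proceed on the fully populated study data".

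The primary ANOVA follows, and then: "A correlation analysis shall be applied to all variable data recorded, as well as key calculations from the data". The reporting rule is "Any correlations scoring a magnitude of 0.85 or greater shall be discussed", with single-factor ANOVA applied to those correlations where appropriate. The section closes its list of interests with "Of primary interest is any impact the starting BMI might have on the amount of change, and any impact that gender may impart". The Statistical Methods paragraph of the SYNOPSIS names the correlation assessment and then states the fill without limit: "Missing or incomplete data shall be populated using least-favorable data from participants who did complete the study". Neither place confines the fill to the waist endpoint.

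Two rules point the other way. The same Statistical methods section opens with "Any patient that did not conclude all three treatments shall be excluded from the analysis". Data quality assurance says that data from patients who discontinue, or whose key data are not properly documented, are left out of the statistical analysis.

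**The concern.** For the mean of one endpoint, giving every dropout the worst completer value can be argued as caution. That argument does not carry over to a correlation or a subgroup contrast, where no direction is the safe one.

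- **Pairs of outcomes.** A patient lost after the third treatment lacks waist change at weeks 1, 4 and 12 and would receive the worst value on each. Outcomes missing together are pulled together by construction.
- **Starting BMI.** BMI stays as observed while the outcome becomes a constant extreme. Dropout unrelated to BMI dilutes a real relation. Dropout related to BMI can create, inflate or cancel one.
- **Gender.** If one sex loses more patients, the inserted values shift that sex's mean.

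The plan singles out BMI and gender and foresees statements based on the correlations. Those statements would partly describe who left and what was inserted, not how patients responded.

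**Working it through.** **Inputs.** From Sample size: SD 1.50 inches, d = 1.0 inch, Z values 1.96 and 0.84. From Recruitment: about 50 recruited and at least 40 completing, hence up to 10 fills if that target is met. From Patient population: roughly even numbers by sex, taken as 25 and 25. Assumptions: normal outcomes, all patients as one pool, least favourable read as the smallest value of each outcome, and dropout unrelated to response.

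**The plan's own figure.** 2 × (1.96 + 0.84)² × 1.5² / 1.0² = 35.28, or 36 after rounding up. A t-based calculation first reaches 80% power at 37 (0.797 at 36, 0.808 at 37), so the stated 37 is reproduced. It enters this point only through the SD and the scale of the trial.

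**Effect of the fill, closed form, 10 fills of 50.** The expected minimum of 40 standard normals is −2.16. The filled share is 0.2.

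- Variance after the fill, in SD² units: 0.8 + 0.2 × 0.8 × 2.16² = 0.8 + 0.747 = 1.547.
- Two filled outcomes with true correlation ρ: r ≈ (0.8ρ + 0.747) / 1.547. For ρ = 0 this is 0.48. For ρ = 0.70 it is 1.307 / 1.547 = 0.84.
- BMI observed, outcome filled, dropout unrelated to BMI: r ≈ 0.8ρ / √1.547 = 0.64ρ. For ρ = 0.43 this is about 0.28, and for ρ = 0.90 about 0.58. Simulation gives 0.27 and 0.57.
- Gender with no true effect: difference in dropout share × 2.16 × 1.5. For 7/3: (7/25 − 3/25) × 3.24 = 0.52 inch. For 8/2: (8/25 − 2/25) × 3.24 = 0.78 inch.

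**Simulation against the 0.85 threshold (40 completers).** Share of trials reaching 0.85:

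| Setting | No fill | 2 fills | 5 fills | 10 fills |
|---|---|---|---|---|
| Two outcomes missing together, true r 0.70 | 1% | 5% | about 19% | about 45% |
| BMI and change, true r 0.90 | about 92% | about 25% | 3% | 0.1% |
| Two unrelated outcomes | 0% | 0% | 0% | 0% |

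With a true r of 0.50 between two outcomes, 10 fills take the pass rate to only 3%.

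**BMI-related dropout (50 recruited, 10 dropouts, log-weight of ±1 per SD of BMI).** A true correlation of 0 becomes about −0.27 or +0.27, with p < 0.05 in 48% of trials. A true correlation of 0.50 becomes about 0.01 or 0.54.

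**Gender, no true effect, 10 fills, one-way ANOVA at 0.05.**

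| Dropout split | Mean spurious difference (inches) | p < 0.05 |
|---|---|---|
| 5/5 | 0 | 0.6% |
| 6/4 | 0.26 | 2% |
| 7/3 | 0.52 | 9% |
| 8/2 | 0.78 | 25% |

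On observed completers the mean difference is about 0 and the error rate about 5% for every split.

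**The case against.** **The fill may not operate.** The Data quality assurance rule and the opening sentence of Statistical methods planned would leave discontinued or incompletely treated patients out, and the analyses in question would then already rest largely on completers. This stands as a condition on the point, but does not remove it. A patient who has all three treatments and is then lost to follow-up is not caught by "Any patient that did not conclude all three treatments shall be excluded from the analysis", yet falls under the fill. The section on data analysis and final reports allows for participants who cannot be contacted or decline follow-up.

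**The 0.85 threshold screens out artefacts.** A reader might infer that unrelated outcomes will be reported as related. The documents do not support that. Unrelated outcomes acquire r of about 0.48 with 10 fills, nominally significant in 97% of trials, but they do not reach 0.85 and so would not trigger the discussion or the ANOVA. The threshold is disturbed only through outcomes already substantially correlated, plausibly repeated waist measurements, and through strong BMI relations pushed below it. Likewise, neither 0.43 nor 0.27 reaches 0.85. The fall in power for that BMI relation, from 81% on 40 observed to 50% on 50 filled, assumes a BMI test that the plan implies by its stated interest but does not specify.

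**Gender error is not generally inflated.** A reader might infer that any dropout produces false gender effects. The fill also inflates variance, so the false-positive rate is below 5% for 5/5 and 6/4 splits. Averaged over dropout unrelated to sex it is 5.0%, and a split as uneven as 8/2 arises by chance in about 7% of trials. Nothing in the documents predicts sex-related dropout. The bias in inches under an unequal split remains.

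**Ten fills is the upper end.** The plan describes its recruitment margin as generous, and every filled patient must have had at least one session. Pain is rated only at treatment sessions, so a patient lost in follow-up has no missing pain score. Both limits are accepted, which is why results for 2 and 5 fills are shown.

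**Conclusion.** Wrong as written, for exploratory analyses. Where the fill operates, the text carries it into the correlation, starting-BMI and gender analyses without exception, and there it distorts in directions that depend on who drops out.

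At 10 fills the distortion is material: about 45% against 1% passing 0.85 for outcomes truly correlated at 0.70; a BMI correlation of 0.90 shown as 0.57 and almost never passing; a gender bias of 0.52 to 0.78 inch under 7/3 and 8/2 splits. At 2 fills the first effect is down to 5%. The sizes rest on normal outcomes, an SD of 1.5 inches, 40 completers and assumed dropout counts. The BMI figures also require dropout unrelated to BMI.

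A reader might infer that the trial's success decision is affected. It is not affected through this route: the primary and secondary criteria in STUDY OBJECTIVES use neither the correlations nor the BMI and gender analyses. Nor do the documents establish that every dropout will be filled, because their exclusion rules say otherwise.

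**What to change.** In Statistical methods planned, and to match in the synopsis, state:

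*Any fill for missing data applies only to the analysis of the waist endpoint. The correlation, starting-BMI and gender analyses use observed values only, with the number of patients shown for each. Baseline BMI and gender of patients without a week-12 value are tabulated beside them.*

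In the same revision, reconcile this with the exclusion in Data quality assurance and the opening sentence of Statistical methods planned, so that one rule says which patients are excluded, which are filled and for which analysis. Without that step the new sentence would sit beside two rules that contradict the fill.

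The cost is wording only, and the new sentence itself leaves the primary analysis unchanged. The downside is small: these analyses would use about 40 rows, not up to 50, and would describe patients with measured outcomes. That can still be biased if dropout depends on response, which is the reason for tabulating the patients without week-12 data.

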**Efficacy of Low-Frequency, High-Intensity Ultrasound  
for Reduction in Subdermal Adipose Layers**

Device Investigated: Ultimate Contour Body Sculpting Device

Indication Studied: Application of ultrasound for non-invasive waist circumference reduction.

A randomized, blinded comparison of waist circumference reduction of an active test group vs. a placebo control in adults.

Sponsor: CAO Group, Inc.

Protocol ID: 005-00036-8

Development Phase: Performance Validation

NCT ID: Not Yet Assigned

Anticipated Initiation Date: 15 December 2019

Anticipated Completion Date: 1 May 2020

Document Date: 10 October 2019

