### **Study configuration**

This study is designed as a single-arm study. All eligible candidates shall be enrolled to undergo treatment by the device according to the procedure and protocol that are discussed herein. This approach is consistent with other studies that have been done with similar devices where the primary objective of waist circumference reduction was also intended.

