### **Sequence and duration of study period**

Patients will be scheduled according to each one's availability for the first of three treatment sessions. After each particular treatment, the patient will be scheduled for the next visit, with it being preferred that subsequent treatments occurring between 6-8 days into the future of the present treatment. Each patient is to receive 3 treatment sessions, with each session featuring the same device settings and conditions of application relative to which study group the patient is assigned to. Overall, the study treatments are anticipated to take about 6 weeks to accomplish. The patient is recalled 1 week, 4 weeks, and 12 weeks after the last treatment for follow-up evaluation.

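### The deciding test is a single-factor ANOVA with no factor named; if the study is single-arm it cannot test the before/after objective, and a paired week-12 analysis should replace it

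*Combined protocol and SAP*

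**What the plan says.** The section on planned statistical methods states: "Primary analysis shall consist of applying the Anova single-factor acceptance test evaluating the change in waist circumference". It adds: "The results of this data shall be directly applied to determining if the primary objective of the study has been met". The level is 0.05. The section gives no factor for the ANOVA, no term for the patient and no statement on pairing.

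The sections that should supply the factor disagree:

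- Title page: "A randomized, blinded comparison of waist circumference reduction of an active test group vs. a placebo control in adults".
- Statistical Methods in the synopsis, with a control group as comparator: "Single factor ANOVA analysis will be used to determine if the extent of circumference reduction in the test group is statistically significant over changes in". Here the factor is group and the response is change.
- Sequence and duration of study period: session conditions are set "relative to which study group the patient is assigned to".
- Study Objectives: the third safety criterion refers to patients in a test group.
- Study configuration: "This study is designed as a single-arm study", with all eligible candidates treated.

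The primary objective is described as a within-patient contrast, "comparing measurements prior to the initial treatment with measurements after the entire treatment regime is concluded", with a reduction of at least one inch required 12 weeks after the last treatment.

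**The concern.** A single-factor ANOVA compares the means of two or more groups. With a control group, the synopsis makes it well defined. With one arm, each patient contributes one week-12 change, all in one group, and the named test has nothing to compare. The analyst would then have to choose a substitute with the data in hand, for the test that decides the trial.

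The choice matters. A substitute that respects the pairing has high power for the sponsor's 1-inch target. One that compares raw waist readings between visits, with no patient term, puts the spread in waist size between patients into the error, although that spread cancels in each patient's own change. Eligibility starts at BMI 25 with no upper limit and covers both sexes, so the spread could be wide.

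**Working it through.** **Inputs.** From Sample size: minimum 40 patients, d = 1.0 inch, σ = 1.50 inches, Z values 1.96 and 0.84. The σ is justified from a reported treatment response, so I read it as the SD of the change. The between-patient SD of waist, s, is not in the documents; I assume 2 to 5 inches.

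**The plan's own figure.** 2 × (1.96 + 0.84)² × 1.50² / 1.0² = 2 × 7.84 × 2.25 = 35.28, or 36 patients. The t-based two-sample version gives 36.3, which rounds up to the stated 37. The formula gives the number per group for two independent groups. It does not describe a single-arm test.

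**What a single-factor ANOVA could be in one arm.**

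1. One week-12 change per patient: one group, so between-group degrees of freedom = 1 − 1 = 0. There is no F statistic.
2. Changes compared across weeks 1, 4 and 12: tests whether the follow-up visits differ. A steady 1-inch loss at all three satisfies the null.
3. Change by sex or BMI class: tests subgroup differences, not the loss. The plan raises these only in its correlation work.
4. Changes against a column of zeros: pooled variance 1.5²/2, so SE = √(1.5²/2 × 2/40) = 0.237 inch. Simulated power is about 98.5%.
5. Raw waist by visit with a patient term (repeated measures): with two visits this is the paired t-test.
6. Raw waist by visit without a patient term: addresses before versus after, but ignores pairing.

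**Paired test.** SE = 1.5/√40 = 0.237 inch and noncentrality = 1/0.237 = 4.22. Two-sided power at 0.05 is 98.4% with 40 patients and 97.6% with 37.

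**Layout 6, baseline against week 12.** SE = s × √(2/40). The observed mean loss must exceed 1.99 × SE (78 df). An SD of change of 1.5 implies a within-patient correlation of 1 − 1.5²/(2s²). Simulated at a true loss of 1 inch, 40 patients:

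| Assumed s (in) | Correlation | SE (in) | Loss needed (in) | Significant |
|---|---|---|---|---|
| 2 | 0.719 | 0.45 | 0.89 | 67% |
| 3 | 0.875 | 0.67 | 1.34 | 12% |
| 3.5 | 0.908 | 0.78 | 1.56 | 3% |
| 4 | 0.930 | 0.89 | 1.78 | 0.6% |
| 5 | 0.955 | 1.12 | 2.23 | under 0.1% |

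With 50 patients the figure is 22% at s = 3 and 1.3% at s = 4. With an SD of change of 2.5 and 40 patients, it is 21% at s = 3 and 4% at s = 4, against 69% for the paired test. When there is no true loss, layout 6 rejects in almost no trials for s of 3 or more, so its risk is a missed effect and not a false claim.

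**The 1-inch criterion.** The paired 95% CI has half-width 2.02 × 0.237 = 0.48 inch. A mean loss of 0.48 inch would therefore already be significant against zero, less than half the required inch. For the whole CI to lie at or above 1 inch, the observed mean loss would have to be 1 + 0.48 = 1.48 inches.

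**The case against.** The synopsis does name a factor, test versus control. The title page, the schedule and the safety criterion fit it, and only Study configuration says otherwise. With a control group, the ANOVA on one change per patient is equivalent to a two-sample t-test and has no dependence problem. That stands: everything about one arm is conditional on Study configuration governing.

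A reader might also infer that visit is the only factor left in one arm, so that repeated readings will be analysed as separate people and a true 1-inch loss will almost never be significant. The documents do not support this. The stated response is the change, not the raw reading. Nothing says that visit is the factor or that readings are entered as independent. Layouts 4 and 5 can also be computed and lose essentially no power. And the low power needs a waist SD that the documents do not give: at 2 inches the visit comparison is still significant in about two thirds of trials. Only at about 3.5 inches or more does it fall to roughly 3% or below.

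The objection does not remove the gap. The section that defines the deciding test specifies none of these layouts, and the literal reading for one arm cannot be computed.

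**Conclusion.** The point holds in conditional form. The firm finding is textual: the primary test has no stated factor and no patient term, and the sections that would supply the factor contradict each other on whether there is a control. If the study is single-arm, an ordinary single-factor ANOVA on one change per patient has zero between-group degrees of freedom and cannot address the before/after objective.

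The loss of power is a risk attached to one possible substitute, not a property of the plan as written. Depending on the substitute, the chance of detecting a true 1-inch loss runs from about 98% (paired, or changes against zero) down to 12% at an assumed waist SD of 3 inches and 0.6% at 4 inches. These figures rest on 40 patients, normal data, σ = 1.50 read as the SD of the change, and the assumed waist SD. Separately, a significant result against zero does not show a loss of at least 1 inch, so naming a paired test alone would not settle the primary objective.

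**What to change.** First reconcile the title page, the synopsis methods, the test-group wording in Study Objectives and the group wording in the schedule with Study configuration.

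If the study is single-arm, replace the primary-analysis sentence with text such as: *The primary analysis is a paired (one-sample) t-test of each patient's baseline-minus-week-12 waist circumference, two-sided at 0.05, reported as the mean change with its 95% confidence interval. Other visits are descriptive.* Then add a sentence on how the result is judged against the 1-inch criterion: for example, whether the observed mean must reach 1 inch together with significance against zero, or whether the lower confidence limit must reach 1 inch. These are very different hurdles, since with the planned SD and 40 patients the second needs an observed mean of 1.48 inches. The sponsor should choose before any data are seen.

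If there is a concurrent control, keep the ANOVA, name group as the factor, and use one week-12 change per patient.

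For the single-arm case the cost is a few sentences, with no extra patients or data. For the controlled case the wording is equally cheap, but the plan's 37 is then a number per group (2 × 37 = 74 completers), and the sample-size section would have to say so.
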